6.2. Secondary objectives

- To describe the best overall response over the treatment duration, determine the duration of tumor response, progression-free survival (PFS), time to treatment failure and overall survival (OS) in each treatment arm.
- To assess safety and tolerability for each treatment arm.

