7. STUDY DESIGN

7.1. Type of study

This is an international open-label, randomized, multicenter phase II study of VIT and VI for the treatment of 80 patients with recurrent or refractory RMS, and 40 additional patient with recurrent RMS only (upon IDMC decision). The study will evaluate the safety and efficacy of these combinations in patients with recurrent or refractory RMS.

The dose of vincristine will be 1.5 mg/m² or 0.05 mg/kg for patient ≤ 10 kg (maximum 2 mg) and will be administered by direct intravenous infusion on day 1 and 8 of each course, before irinotecan.

The dose of irinotecan will be 50 mg/m²/d. Irinotecan will be given intravenously infusion over 1 hour on days 1-5 of each course, one hour following the administration of TMZ.

In the absence of any contraindication (ie known allergies), treatment with oral cefixime 8 mg/kg once daily (maximum daily dose 400 mg) is recommended and will be started 2 days before chemotherapy until day 7 (see Appendix 11 for cefixime management in The Netherlands).

TMZ will be given according to the randomization. The starting dose of TMZ will be 125 mg/m²/d. The dose of TMZ will be escalated to 150 mg/m²/day at cycle 2 for patients who do not experience ≥ grade 3 toxicity of any kind. TMZ will be given orally, on an empty stomach, on days 1 through 5 of each course. The capsules must be swallowed whole with a glass of water. For young children and patients who have difficulty swallowing capsules, the full daily dose of TMZ capsules should be placed in 10-30 ml fruit juice or compote and administered after the capsules have been allowed to soften for 15-20 minutes.

Dose reductions and/or administration delays will be performed using specific predefined rules to accommodate individual patient tolerance of treatment and to maintain optimal dose intensity (section 8.3.5.).

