9. TREATMENT ADMINISTRATION

9.1. Starting doses and schedules

ARM A		
D1 and D8 Vincristine	1.5 mg/m ² /d – IV bolus (0.05 mg/kg for patient ≤ 10 kg)	3 weekly
D1 to D5 Irinotecan	50 mg/m ² /d – IV over 1 hour	3 weekly
ARM B		
D1 to D5 Temozolomide	125 mg/m ² /d - PO	3 weekly
D1 and D8 Vincristine	1.5 mg/m ² /d – IV bolus (0.05 mg/kg for patient ≤ 10 kg)	3 weekly
D1 to D5 Irinotecan	50 mg/m ² /d – IV over 1 hour	3 weekly

Vincristine: The dose of vincristine will be 1.5 mg/m² or 0.05 mg/kg for patient ≤ 10 kg (maximum 2.0 mg) and will be administered by direct intravenous infusion on day 1 and day 8 of each course, before irinotecan. Administration must comply with guidance on administration of vinca alkaloids as per NPSA/2008/RRR004.

Irinotecan: The dose of irinotecan will be 50 mg/m²/day. Irinotecan will be given intravenously infusion over 1 hour on days 1-5, one hour following the administration of TMZ. In absence of contraindications (known allergies), **systematic treatment with oral cefixime 8 mg/kg once a day (maximum daily dose 400 mg) is recommended and will be started 2 days before chemotherapy until day 7** (see Appendix 11 for cefixime management in The Netherlands).

Temozolomide: will be given according to the randomization: The starting dose of TMZ will be 125 mg/m²/day. The dose of TMZ will be escalated to 150 mg/m²/day at cycle 2 for patients who do not experience ≥ grade 3 toxicity of any kind. The dose of TMZ should be rounded to the nearest 5 mg. TMZ will be given orally, on an empty stomach, prior to vincristine and irinotecan, on days 1-5 repeated every 3-weeks. If the patient vomits within 20 minutes after TMZ, the dose will be re-administered. The capsules must be swallowed whole with a glass of water. For young children and patients who have difficulty swallowing capsules, the full daily dose of TMZ capsules should be placed

in 10-30 ml fruit juice or compote and administered after the capsules have been allowed to soften for 15-20 minutes or according to normal local practice for patients in the United Kingdom (see Appendix 12).

Treatment will continue until disease progression, unacceptable toxicity or the patient's desire to discontinue therapy. Local treatment is allowed after 2 cycles.

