Patients must have evidence of recovery from all prior cycle toxicity and the ANC must be > 1000/mm³ and platelets > 100 000/mm³ before receiving the next cycle of therapy. If initiation of the next treatment cycle is delayed by more than 2 weeks, the patients should be discontinued from the study.

In the absence of clinically progressive disease, patients should receive at least 2 cycles of VIT or VI prior to the first evaluation on study treatment.

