10.2.3 End of study treatment / Withdrawal procedures

The duration of study participation is a maximum of 12 cycles. However, the continuation of treatment can be individually discussed with the investigator for patients who do not experience progression of disease after 12 cycles.

The following evaluation is performed 3 weeks after the last cycle of chemotherapy or at the end of study (see 7.2.).

Type of Assessment	Delay for End of Study treatment or Withdrawal

CLINICAL EXAM
 
 • Full physical examination • height, weight, body surface • Vital signs : blood pressure after 5 min at rest, heart rate, temperature • Performance status (Lansky Play Score or Karnofsky Score – appendix 3-4) • Assessment of adverse events according to the NCI-CTC AE v.4.0 (appendix 5) • Recording of concomitant medications 	
To be performed 3 weeks after the last cycle of chemotherapy or at the end of study

LABORATORY TESTS
 
 • Complete blood count : white count (WBC), hemoglobin (HGB), hematocrit (HCT), differential count and platelet count • Serum chemistries : glucose, urea, creatinine, total protein, albumin, Ca+, phosphorus and electrolytes (sodium, potassium, chloride and bicarbonate), AST, ALT, total bilirubin, alkaline phosphatase, LDH, GGT 	
To be performed 3 weeks after the last cycle of chemotherapy or at the end of study

RADIOLOGICAL AND OTHER INVESTIGATIONS
 
 • Tumor assessments (CT scan and/or MRI) including measurement of target lesion and assessment of response to treatment should be loaded the CDs onto the PACS system for later review. • Bone scan or FDG-PET Scan* • BM aspirates and trephine biopsies* 	
Mandatory
 
To be performed 3 weeks after the last cycle of chemotherapy or at the end of study, except documented previous disease progression

**only repeated if clinically indicated or if initially involved or to confirm tumor response*

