11.1.3. Objective tumour response and progression

Primary efficacy endpoint

The primary efficacy endpoint is defined as the proportion of patients who had a documented complete or partial tumour response occurring after the first 2 cycles of treatment which must be confirmed by a follow-up objective tumour assessment obtained within 4-5 weeks after the initial documentation.

Secondary endpoints

Secondary efficacy endpoints are defined as follows:

- The best overall response is the best response recorded from the start of the treatment until disease progression/recurrence (taking as reference for PD the smallest measurements recorded since the treatment started) over the whole treatment duration. It must be confirmed by a follow-up objective tumour assessment obtained within 4-5 weeks after the initial documentation.
- Duration of tumour response: the time from first documentation of objective tumour response to the first objective or clinical documentation of progression
- Time to treatment failure: the time from the date of first treatment administration to the first documentation of tumour progression, discontinuation of study treatment before one year, or death, whichever occurs first
- Progression-free survival (PFS): the time from the date of first treatment administration to the date of first objective or clinical documentation of tumour progression or death due to any cause
- Overall survival (OS): the time from the date of first treatment administration to date of death

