Appendix 1 – Scheme of the Study of treatment

Systematic treatment with oral cefixime 8 mg/kg once a day (max daily dose 400 mg) is recommended and will be started 2 days before chemotherapy until day 7 (see Appendix 11).

Repeated 3-weeks cycles until disease progression, unacceptable toxicity or the patient's desire to discontinue therapy

- * The dose should be rounded off the nearest 5 mg. The dose will be escalated to 150 mg/m² at cycle 2 for patients who do not experience ≥ grade 3 toxicity (NCI-CTCAE v4.0). For patients who have difficulty to swallowing or young children, the daily dose of temozolomide capsules should be placed in 10-30 ml fruit juice or compote and administered after the capsules have been allowed to soften for 15-20 minutes. If the patient vomits within 20 minutes after TMZ, the dose will be re-administered.
- ** The dose will be 1.5 mg/m² or 0.05 mg/kg for patient ≤ 10 kg (max 2 mg), and will be administered by direct intravenous infusion on day 1 of each course, before irinotecan. Administration must comply with guidance on administration of vinca alkaloids as per NPSA/2008/RRR004.
- *** The dose will be 50 mg/m² and will be administered by 60 min intravenous infusion one hour following the administration of temozolomide

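### Time to treatment failure: read literally, the one-year stopping rule counts a progression-free patient who completes the stated 12-cycle maximum on schedule as a failure

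*Protocol*

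**What the plan says.** - **TTF definition (Protocol 11.1.3, Secondary endpoints).** TTF runs from the first treatment administration to the earliest of documented progression, "discontinuation of study treatment before one year, or death, whichever occurs first". Completing the planned course is not mentioned.
- **Treatment duration (10.2.3).** "The duration of study participation is a maximum of 12 cycles". The next sentence adds that "the continuation of treatment can be individually discussed with the investigator for patients who do not experience progression of disease after 12 cycles".
- **Treatment rule elsewhere.** Section 9.1 says "Treatment will continue until disease progression, unacceptable toxicity" or the patient's wish to stop, and Appendix 1 says "Repeated 3-weeks cycles until disease progression, unacceptable toxicity" or the patient's wish. Neither mentions a 12-cycle limit.
- **Delays (9.1).** A patient comes off study "If initiation of the next treatment cycle is delayed by more than 2 weeks", so each interval between cycles may stretch by up to 14 days.
- **Role of TTF.** Section 6.2 lists "progression-free survival (PFS), time to treatment failure and overall survival (OS) in each treatment arm" among the secondary objectives. The comparative objective in 6.3 names only response rate, PFS and OS. After amendment 5.0, section 12.2 extends the VIT versus VI comparison to all efficacy and safety endpoints, which brings TTF in.

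**The concern.** A treatment-failure endpoint should count stopping that signals failure: progression, toxicity, refusal or death. Here the limit is set in calendar time at one year, while the stated maximum course, given on schedule, ends well before that. Taken as written, the clause counts as failures the very patients who did best, those who completed every cycle without progressing.

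It also makes the outcome depend on a decision. Section 7.1 says "This is an international open-label, randomized, multicenter phase II study of VIT and VI", so the discussion about continuing past cycle 12 takes place with the arm known. Two patients with the same disease course can receive opposite TTF status according to how that discussion ends.

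What is at stake is the late part of the TTF curve and any rate read from it, such as a rate at one year. Two analysts could also produce different curves from the same data, depending on what they take discontinuation to mean.

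**Working it through.** The protocol gives no figure for this point, so there is none to reproduce. The check is calendar arithmetic.

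**Inputs**
- Cycle length: 21 days (10.2.2; 10.2.1 agrees, with two cycles as weeks 1 to 6).
- Stated maximum: 12 cycles (10.2.3).
- Last dosing day in a cycle: day 8, vincristine (9.1).
- Maximum delay: 14 days at each of 11 intervals (9.1).
- TTF origin: first administration (11.1.3). One year is taken as 365 days.

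**On-schedule course**
- Last dose of cycle 12: 11 × 21 + 7 = 238 days after first dose = week 34.0.
- End of cycle 12: 12 × 21 = 252 days = week 36.0.
- One year in cycles: 365 / 21 = 17.4.
- Gap to one year: 365 − 252 = 113 days if the stop is dated at the end of the cycle; 365 − 238 = 127 days if dated at the last dose.

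**Delays needed to escape the event without continuing past cycle 12**
- Stop dated at end of cycle 12: 113 / 11 = 10.3 days on average at every interval.
- Stop dated at last dose: 127 / 11 = 11.5 days on average at every interval.
- At the full 14 days each time, cycle 12 ends at 252 + 11 × 14 = 406 days, past one year.

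**Upper bound on the effect**

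By one year, a completer who stops on schedule loses at most 113 to 127 days of failure-free time. For each percentage point of patients who complete and stop, mean TTF restricted to one year falls by at most 0.01 × 113 = 1.1 to 0.01 × 127 = 1.3 days.

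**Illustration, on assumed values only**

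Let S be the proportion still progression-free on treatment at week 34, and q the share of them who continue past cycle 12. With no delays, the literal curve falls from S to at most S × q.

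| S | q = 0 | q = 0.25 | q = 0.50 |
|---|---|---|---|
| 0.10 | 0.00 | 0.025 | 0.05 |
| 0.20 | 0.00 | 0.05 | 0.10 |
| 0.30 | 0.00 | 0.075 | 0.15 |

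The protocol gives neither S nor q, so the actual drop cannot be derived.

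**Median**

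For on-schedule patients, the literal and corrected definitions give the same events until week 34. If fewer than half complete 12 cycles, the curve has already passed 0.5 by then and the median is the same under both.

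**The case against.** The strongest reply is that the clause was never meant to catch completers. The dose-modification tables in 9.2.1 and the delay rule in 9.1 speak of discontinuing for toxicity or delay. Section 7.8 does not list completing 12 cycles as a reason for withdrawal, and the heading of 10.2.3 names end of treatment separately from withdrawal. A one-year limit is compatible with this: it may simply mark when stopping ceases to count. That reading is reasonable, but no section states it, so the ambiguity stands.

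Two stronger readings are tempting and are not supported:

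- **That the TTF curve is cut off after week 34.** Section 10.2.3 allows continuation, 9.1 and Appendix 1 state no cap, and permitted delays can carry cycle 12 to day 406. The curve is pulled down by those who complete and stop on or near schedule. It reaches zero only if nobody continues or is sufficiently delayed.
- **That one year corresponds to no possible course.** It lies within the range that delays allow (252 to 406 days) and within the open-ended rule in 9.1. What holds is that it does not match the stated maximum given on schedule.

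It is also fair to say that the protocol plans no restricted mean and names no one-year TTF rate. Section 12.2 speaks of Kaplan-Meier estimates and medians, and the median is probably the least affected summary.

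**Conclusion.** The point holds as a minor defect in a secondary endpoint. The one-year limit in 11.1.3 and the 12-cycle maximum in 10.2.3 do not fit together, and the literal text scores an on-schedule, progression-free completer who stops as a failure at week 34 to 36. The effect is confined to the TTF curve from about then on, and its size cannot be computed from the protocol.

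This rests on 21-day cycles, a literal reading of discontinuation, and a stop at or near schedule without continuation. The statement about the median assumes on-schedule courses and sets censoring aside.

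A reader might infer that the comparison of VIT with VI is biased in a known direction. The documents do not support that: they do not say how many patients in each arm reach cycle 12 or continue beyond it. The response endpoint, the rule of 22 successes among 47, PFS and OS do not use this clause, and no decision rule uses TTF.

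**What to change.** In 11.1.3, replace the one-year clause with: *discontinuation of study treatment for any reason before completing 12 cycles*. Add: *Completing 12 cycles without progression is not an event; such patients remain at risk for progression or death.* As optional tidying, refer to the 10.2.3 maximum in 9.1 and Appendix 1.

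No new data are needed. Section 13.9 already requires cycle dates and the date and reason of discontinuation in the eCRF, and 10.2.4 continues tumour assessment every 3 months after treatment.

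There are two downsides. After cycle 12, TTF equals PFS for completers, and toxicity stops in patients who continue beyond cycle 12 no longer count.

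Timing also matters. The version history for version 5.1 (June 2019) shows that differences between the arms in OS and PFS were already under discussion, so the change would come after comparative results were known. The literal one-year definition should therefore be reported alongside as a sensitivity analysis.

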7.7. Patient enrolment

According to the Good Clinical Practice (GCP) guidelines, all inclusion/exclusion criteria will be checked during the registration procedure. A registration number that further identifies the patient within the centre will be allocated to the patient.

The following procedures should be performed before completing the registration form:

- Informed consent leaflet should be signed by patient or the parents or legal representative of patient and the investigator before starting any study procedure ;
- All selection procedures should be performed as per protocol ;
- After patient registration, the patient identification number and treatment arm allocated will be retained within the study even if the patient is withdrawn from the study before the first study drug administration. New patients must always be allocated a new number.

The procedure for enrolling patients will be detailed for each participating centre. The TenAlea software program via internet will be the preferred system. It is possible to use a backup procedure by faxing the registration form to the following address:

Clinical Research Integrated Unit / Sponsor Unit

Centre Oscar Lambret – Lille - France

[contact] - [contact]

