7.8. Withdrawal from study treatment

Patients will be considered withdrawn from study for one of the following reasons:

- Progressive disease
- Global deterioration of health status
- Unacceptable toxicity (Noted on CRF adverse event page)
- Cycle of treatment delayed by more than 2 weeks
- Investigator decision
- At the request of the patient or a representative
- Lost to follow up
- Death of patient

This section only concerns treatment withdrawal, since the main statistical analysis will be performed on the intent to treat patient population. Follow-up visits are planned after “withdrawal from study treatment”.

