The main analysis will be performed on the intent to treat principle, considering all patients included in the study. Patients who withdraw from the study will be accounted for up until the time they withdraw from the study. Secondary analyses will be performed on the per protocol population, that is eligible, evaluable and treated patients. Safety analyses will be performed on all treated patients. Eligible patients are defined as patients who did not have a major violation of eligibility criteria (inclusion and exclusion criteria).

Treated patients are defined as patients who received at least one injection of the study treatment.

Evaluable patients for main objective (objective response at 2 cycles) are defined as patients who received at least 2 cycles of the study treatment and whose the tumor evaluation at 2 cycles was available.

The estimated difference in response rates between the two arms, will be presented with a 90% confidence interval. A Bayesian analysis of the final data will also be performed in which probabilities that one arm is better than the other will be given.

The risk / benefit ratio will be examined biannually by the IDMC on validated data. The sponsor may decide to temporarily halt recruitment to the trial if the rate of severe toxicities significantly exceeds 15%.

The decision rules for early termination are applied to the VIT arm as the VI arm is only used for controlling selection bias. However, at the end of the trial, if the VIT arm is considered sufficiently active, a phase III trial may be initiated. If the VIT arm is considered insufficiently active, this treatment strategy is rejected and other options should be considered. The cut points for acceptable and unacceptable response rates, obtained from the Optimum Simon design, will be used as guidelines for deciding whether VIT is worthy of further investigation; the response rate in the VI arm, the toxicity of the regimens and relevant external evidence will also be taken into consideration. Categorical variables will be presented as frequencies and percentages. Continuous variables will be presented as means (standard deviation), and medians (range). The treatment groups will be compared for demographic and initial disease characteristics using Fisher's exact test for categorical variables and the non-parametric Wilcoxon test for continuous variables.

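### PFS, OS and TTF start at first dose, so the ancillary VIT versus VI survival comparison has no place for randomised patients who are never dosed

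*Protocol*

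**What the plan says.** **Time origin.** Protocol section 11.1.3 (Secondary endpoints) defines PFS as "the time from the date of first treatment administration to the date of first objective or clinical documentation of tumour progression or death" and OS as "the time from the date of first treatment administration to date of death". The TTF entry opens "Time to treatment failure: the time from the date of first treatment administration to the first documentation of tumour progression" and goes on to include treatment discontinuation within the first year and death.

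**Patients never dosed.** Section 7.7 says that the identification number and the allocated arm "will be retained within the study even if the patient is withdrawn from the study before the first study drug administration". Such patients are foreseen, and they are kept.

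**Population.** Section 12.2 (Statistical analyses) states: "The main analysis will be performed on the intent to treat principle, considering all patients included in the study". Section 7.8 says that "the main statistical analysis will be performed on the intent to treat patient population". Section 12.2 defines treated patients as a separate set, those with at least one injection, and assigns that set to safety. The per-protocol set is reserved for secondary analyses.

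**Use of the endpoints.** Section 6.3 adds, from amendment 5.0, an ancillary objective: the relative effect of VIT against VI on response rate, PFS and OS. Section 12.2 implements it for all efficacy endpoints, with stratified logrank tests and Cox hazard ratios for OS and PFS. It gives no population of its own for this comparison and no alternative start date.

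**Duration of response.** The same list in section 11.1.3 defines it as "the time from first documentation of objective tumour response to the first objective or clinical documentation of progression".

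**The concern.** A comparison of randomised arms is protected by randomisation only if it follows every randomised patient from the moment of allocation. Here the clock starts later, at an event that some patients may never reach. They cannot be placed on a PFS, OS or TTF curve, and a death between allocation and first dose is not counted.

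The trial is open-label and the arm is known before dosing, so failure to start treatment could depend on the arm. If it did, the comparison would be between two selected groups.

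First-dose origin is defensible when each arm is only described, as in section 6.2. It is a poorer fit now that PFS and OS are compared between arms. Section 12.1 also records that the extra 40 patients were added partly for precision on the secondary endpoints and to help choose the standard arm for the next trial.

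**Working it through.** The point rests on definitions, and the protocol states no figure to reproduce. The check sets the provisions side by side.

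1. Section 7.7: a patient allocated to an arm and withdrawn before the first dose stays in the study under that arm.
2. Section 12.2: the lead analysis takes in all included patients, so this patient belongs to it. The treated set excludes this patient, but the protocol uses that set for safety.
3. Section 11.1.3: PFS, OS and TTF each equal an end date minus the date of first administration. For this patient the second term does not exist, so none of the three has a value.
4. Sections 6.3 and 12.2: these endpoints feed a between-arm comparison, and no substitute start date is given anywhere in the protocol.
5. It follows that the comparison, carried out as written, contains treated patients only.
6. The primary endpoint in section 11.1.3 is a proportion of patients with confirmed response. It uses no start date, so steps 3 to 5 do not touch it.

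**Size, under an assumption.** The protocol gives no count of never-dosed patients. Assume 1 to 3 in one arm.

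| Denominator | Source | 1 patient | 3 patients |
|---|---|---|---|
| 60 per arm | 120 / 2, section 12.1 with 1:1 allocation | 1/60 = 1.7% | 3/60 = 5.0% |
| 54 per arm (relapse patients) | 108 / 2, section 12.1 | 1/54 = 1.9% | 3/54 = 5.6% |

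With 1 to 6 such patients over both arms, 1/120 = 0.8% to 6/120 = 5.0% of all randomised patients would have no PFS, OS or TTF value.

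**Duration of response.** In one list, PFS and TTF both include death as an event, while duration of response names progression only. A responder who dies without documented progression has no end event under that definition.

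**The case against.** **Reach of intent to treat.** A reader might infer that the protocol labels its PFS and OS analyses intent to treat and then excludes patients from them outright. The text does not go that far. The label is attached to the main analysis, which section 7.2 ties to end-of-treatment imaging and separates from the final survival analysis five years after the last recruitment. Section 12.2 names no population for OS and PFS, and no sentence orders exclusion. This objection stands as a limit on the wording. The inference is still reasonable, because all included patients is the only lead efficacy population given. The loss of never-dosed patients follows from the definitions alone.

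**Weight of the endpoints.** The decision rule uses responses in the VIT arm. PFS, OS and TTF are secondary, and the comparison is ancillary. This stands in full.

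**Likelihood of bias.** Selection procedures precede registration. Clinical and laboratory checks fall within a week of the planned start, so the planned gap to first dose is short. Entry requires a performance score of at least 70 and a life expectancy of at least 12 weeks. The arms share vincristine and irinotecan and differ by an oral drug. Arm-dependent failure to start is possible, but nothing in the protocol shows that it is material. Nor does the protocol support assuming that never-dosed patients would mostly have early events.

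**The 15% allowance.** A reader might take the 15% in section 12.1 as an upper bound on the loss. It covers ineligible and non-evaluable patients. Evaluable means at least two cycles received with the two-cycle assessment available, so the allowance includes patients who were dosed. It says nothing about those who never were.

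**Deaths in responders.** A reader might say that the protocol censors them. It states no such rule, and the analysis plan, which is not shown, may settle it. Clinical progression already counts as an end event, so the group concerned is narrow. What remains is that the definition omits an event which its neighbours include.

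**Conclusion.** The point holds in a limited form. The first-dose origin cannot be combined with analysing all randomised patients, so the ancillary VIT versus VI comparison of PFS, OS and TTF is, as written, a comparison of treated patients. An analysis plan could override the definition, but it would have to contradict what the protocol fixes.

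The effect is probably small: 1.7% to 5% of an arm of about 60 if 1 to 3 patients go undosed. Those counts are assumed. The direction of any bias cannot be stated from the document. The primary response endpoint and the decision rule built on it are not affected.

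The duration-of-response wording is a separate, minor matter, and its size cannot be derived from the protocol.

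**What to change.** - For the VIT versus VI comparison, define PFS, OS and TTF from the date of randomisation in all randomised patients. State how never starting treatment counts for TTF.
- Keep first-dose origin as a sensitivity analysis in treated patients.
- Document the change with its date and reason, and report both versions. The version history entry for version 5.1 already refers to a larger VIT effect on OS than on PFS, so comparative results had been seen and the choice of origin should be open to inspection.
- Report the number of never-dosed patients by arm.
- Separately, add death from any cause as an end event for duration of response.

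The cost is a change of wording. Arms are allocated through the registration system, so randomisation dates should already exist. Times lengthen by the gap from randomisation to first dose, which is planned to be under about a week. No new data collection should be needed for treated patients. Never-dosed patients need their progression and survival follow-up, and where it was not collected that should be stated.
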